4. STUDY DESIGN

4.1. Type and design of the study Pilot study of phase I, open, two-branch, **multicentre** clinical trial for the study of the efficacy of passive immunization through repeated infusion of plasma from people exvalescing from infection with COVID-19 and/or with a negative viremia result for COVID-19, together with the standard treatment that is currently being scheduled, compared to the exclusive application of standard treatment in currently hospitalized COVID-19 patients. **The study will be carried out and coordinated by HUSLL, which may be joined by all health centres interested in participating in the study that meet the requirements to be able to develop it and commit to the conditions of the same. In each centre, the study subjects will be selected among those admitted to both the COVID-19 plant and the ICU (or their counterpart places in each centre).** Below is an outline of the study design:

[figure not shown]

Fig 1. Outline of the design of the study protocol to be carried out.

IMPORTANT NOTE: the scheme refers to the coordinating centre (HUSLL), but the same conditions are extended to all those centres participating in the multicentre study.

The assignment to the control and intervention groups, both in the plant and in the ICU, will be done by means of simple random assignment, using equiprobability calculations through a computer system, in order to guarantee that all subjects have the same probability of belonging to the two groups. The system will be the same in all participating centres. This system will be carried out whenever a plasma stock is available. In the event that the stock runs out, the recruited patients will be part of the control group.

The characteristics of the experimental groups are detailed below:

-For intervention group: usual standard treatment (according to clinical guideline for COVID-19), plus two infusions followed by a volume equal to 300 ml of plasma from patients convalescing from COVID-19 and with negative viremia in the COVID-19 detection test and therefore discharged and / or cured. The infusions will be given on days 1 and 2 of study, after the positive result for COVID-19 of the recipient patient, who will be treated.

-For control group: usual standard treatment, according to clinical guideline for COVID-19. This is based on any drug used in clinical practice accepted to date, from retroviral (lopinavir/ritonavir;

darunavir/cobicistat; remdesivir), interferon- α/β , anti-IL-6 monoclonal antibody (Tocilizumab) or oxygen therapy among others. The ratio controls: treated will be 1:2 in favour of the treatment. As treatments have been changing throughout the pandemic, when performing the final analysis, a stratified analysis will be made by type of treatment. That is, infected patients who have been treated with the same drugs will be compared.

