4.2. Patient selection

4.2.1. Inclusion criteria

Plasma donors may be selected from among patients already discharged for COVID-19 in the centres participating in the study (who have not received plasma), as well as by volunteers who meet the requirements for inclusion and non-exclusion, who wish to donate and go to HUSLL or the blood and tissue bank of the Balearic Islands.

The study sample for both the intervention and control group will be extracted from patients who are positive in the real time-polymerase chain reaction (RT-PCR) test for the detection of COVID-19, in any of the participating centres (admitted to the plant or ICU), and who meet the inclusion and non-exclusion criteria, and voluntarily wish to participate, after being informed with the Patient Information Sheet (HIP), and have signed the informed consent (IC).

Both donors and study subjects will be provided with the specific HIP and IQ. Each participating centre will sign a participation agreement, confidentiality commitment and transfer of study results for further analysis, following the usual logistics guidelines of multicentre studies.

1. Below are the inclusion criteria:

For the receiver:

A. Recipients hospitalized in COVID-19 floor:

1. Ability to understand the HIP and sign the IQ of the study.
2. Age greater than or equal to 18 years, male or female.
3. Patient hospitalized in COVID-19 floor (or equivalent areas in each centre) with COVID-19 diagnosis by PCR in nasopharyngeal smear or in any other biological sample.

4. Presence of respiratory symptoms and / or fever associated with COVID-19, with time of evolution of the clinic by COVID-19 equal to or less than 7 days (being day 1 the day of onset of symptoms and including day 7).
5. Presence of pneumonia in chest x-ray and/or $\text{SatO}_2 < 94\%$ aa.
6. Sequential Organ Failure Assessment score (SOFA) ≤ 6 .
7. Accept the condition of complying with the procedures established in the protocol.
8. That you will remain admitted at least 5 days at the discretion of the clinician, in order to perform the procedures correctly.

B. Recipients hospitalized in ICU:

1. Ability to understand the HIP and sign the IQ of the study. **In case of impossibility of signing IC (e.g., intubated patients) the oral IC will be accepted.**
2. Age greater than or equal to 18 years, male or female.
3. Patient hospitalized in ICU with COVID-19 diagnosis by PCR in nasopharyngeal smear or in any other biological sample.

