4. Presence of respiratory symptoms and / or fever associated with COVID-19, with time of evolution of the clinic by COVID-19 equal to or less than 7 days (being day 1 the day of onset of symptoms).
5. Sequential Organ Failure Assessment score (SOFA) > 6 .
6. Accept the condition of complying with the procedures established in the protocol.
7. In addition, for ICU patients, the criteria for admission to the ICU that has been given by the Ministry of Health and the Spanish Society of Intensive Care Medicine will be considered (**updated to the current situation**). A summary is attached to the following table, and more information is added in Annex IX (also available www.semicyuc.org · www.fepimeti.org · www.seeeiuc.org).

MAJOR CRITERIA (1 criterion necessary)
Septic shock with the need for vasoactive drugs
Respiratory failure requiring mechanical ventilation
MINOR CRITERIA (3 or more criteria)
Respiratory rate > 30 breaths/minute with conventional oxygen therapy
$\text{Pao}_2/\text{FiO}_2 < 250$ with conventional oxygen therapy
Bilateral infiltrates
Altered level of consciousness
Elevation of urea ($< 20\text{mg/DL}$)

Leukopenia (<4000 cells/ml) and lymphopenia
Thrombocytopenia (<100000/ml)
Hypothermia (<36°C)
Hypotension requiring aggressive resuscitation with fluids
D-dimer > 1 µg/L

In case of overflow situation, the following triage tool will also be considered, based on the use of the SOFA.

Colour Code	Initial Assessment	48 hour Assessment	120 hour Assessment	Priority/Action
Blue	Exclusion Criteria* or SOFA > 11*	Exclusion Criteria Or SOFA > 11 Or SOFA 8 – 11 no	Exclusion Criteria* or SOFA > 11* or SOFA < 8 no	Medical Mgmt +/- Palliate & d/c from critical care
Red	SOFA 7 or Single Organ Failure	SOFA score < 11 and decreasing	SOFA score < 11 and decreasing progressively	Highest
Yellow	SOFA 8 – 11	SOFA < 8 no	SOFA < 8 with < 3 point decrease in past 72h	Intermediate
Green	No significant organ failure	No longer ventilator dependant	No longer ventilator dependant	Defer or d/c, reassess as needed

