5. DATA ANALYSIS: STATISTICS

A descriptive analysis of all variables will be performed. With the categorical variables, the global percentages and frequencies will be estimated. Normality tests and graphs will be used to determine if the quantitative variables follow a normal distribution. Normal distribution variables shall be expressed as mean \pm standard deviation and those without normal distribution shall be expressed as median and interquartile range. To describe the significance and associations between variables after the intervention, parametric and non-parametric tests will be used as appropriate (the student's t test of paired samples or the Wilcoxon test for quantitative variables and the ANOVA test for paired samples or Friedman test for qualitative variables). The correlations will be examined by the correlation of Spearman or Pearson ranges and a multivariate analysis will be performed to assess the effect of other factors such as the confusion/interaction effect, as well as to assess the possible construction of predictive models. A p-value $< 0,05$ shall be considered an indicator of a significant difference. SPSS v.23 software will be used for data analysis.

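### Simple randomisation across ward, ICU and several centres, with location, SOFA, symptom-onset date and centre missing from the database list, gives up balance and precision that would be cheap to keep

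*Combined protocol and SAP*

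**What the plan says.** **Assignment (section 4.1).** One procedure covers ward and ICU patients alike: allocation "will be done by means of simple random assignment, using equiprobability calculations through a computer system". The stated aim is "in order to guarantee that all subjects have the same probability of belonging to the two groups". On centres: "The system will be the same in all participating centres". The text describes no blocks, strata or minimisation (Fig 1 is not shown). Later in the same section the ratio is given differently: "The ratio controls: treated will be 1:2 in favour of the treatment".

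**Populations (section 4.2.1).** Ward recipients need SOFA ≤ 6 and ICU recipients SOFA > 6. Both need symptoms of at most 7 days; the ward criterion counts this as "being day 1 the day of onset of symptoms and including day 7".

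**Data (section 4.3.3, Table 1).** There is no entry for ward or ICU at baseline, SOFA, date of symptom onset or centre. The date of diagnosis is listed. ICU admission appears only as a percentage among the clinical outcomes. Severity measures that are listed include the WHO progression scale, PSI, oxygen saturation, PO2 and ECOG.

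**Analysis (sections 4.1 and 5).** Section 5 says that "a multivariate analysis will be performed to assess the effect of other factors", without naming covariates. The only stratified analysis planned, in section 4.1, is by drug treatment.

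**Enrolment (Annex IX).** The inclusion email carries the names of the investigator and treating doctor and the consent date. It does not carry the patient's location.

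**The concern.** The protocol combines two groups that its own criteria separate by severity, and severity at entry is likely to drive mortality, length of stay and the WHO scale. Simple randomisation does not hold the ICU share equal between arms, even if it is run separately on the ward and in the ICU. Adjustment in the analysis is the usual second safeguard. Here the factors that would be adjusted for first are not on the list of data to be analysed, although three of them have to be established at screening to judge eligibility and the fourth, centre, is always known.

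At stake are the precision of the between-arm estimate and its credibility if the arms visibly differ in ICU share.

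**Working it through.** The documents give no sample size, event rate or effect size, so there is no planned figure to reproduce. The check is how often simple randomisation leaves the arms apart, and what adjustment is worth.

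**Inputs**
- Probability of treatment: 1/2 (equal probability) or 2/3 (the 1:2 ratio). Section 4.1 supports both, so both were run.
- ICU share q: not stated for the trial. Section 2 gives about 10% of admitted patients; 10–30% is assumed.
- N: not stated; 30, 60, 100 and 200 are assumed.
- Mortality: 40% in ICU and 10% on the ward, assumed for illustration.

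**1. Imbalance in ICU share.** Let T_I ~ Bin(qN, p) and T_W ~ Bin((1−q)N, p) be the treated numbers in ICU and ward. The imbalance is

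|T_I/(T_I + T_W) − (qN − T_I)/(N − T_I − T_W)|.

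Chance of a difference of 10 points or more (each cell: 1:1, then 1:2):

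| N | q = 10% | q = 20% | q = 30% |
|---|---|---|---|
| 30 | 34%, 51% | 54%, 58% | 61%, 65% |
| 60 | 22%, 23% | 34%, 38% | 42%, 46% |
| 100 | 10%, 12% | 21%, 25% | 29%, 30% |
| 200 | 2%, 3% | 8%, 10% | 13%, 15% |

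For 15 points or more the ranges are 25–46% at N = 30, 5–26% at N = 60, 1–13% at N = 100 and at most 3% at N = 200.

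**2. Effect on a crude comparison.** Shift in the risk difference = imbalance × (ICU risk − ward risk). With a 30-point gap in risk, a 10-point imbalance shifts it by 0.10 × 0.30 = 3 points and a 15-point imbalance by 0.15 × 0.30 = 4.5 points.

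**3. Value of adjusting for location.** The share of outcome variance explained is R² = q(1−q)(0.40 − 0.10)² / [m(1−m)], where m = 0.40q + 0.10(1−q). The gain, expressed as equivalent extra patients, is 1/(1−R²) − 1.
- q = 10%: m = 0.13; R² = 0.0081/0.1131 = 0.072; gain 1/0.928 − 1 = 8%.
- q = 1/3: m = 0.20; R² = 0.02/0.16 = 0.125; gain 1/0.875 − 1 = 14%.

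**4. With stratified blocks.** Permuted blocks within ward and ICU (size 4 for 1:1, size 6 for 1:2) bring the chance of a difference of 10 points or more to 0 at N = 60, 100 and 200 for every q above. At N = 30, incomplete blocks leave 0–40% for 10 points or more, at most 8% for 15 points or more and 0 for 20 points or more.

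**5. What the listed data can replace.** The WHO scale separates levels of oxygen support but does not identify location, since three minor criteria suffice for ICU entry without ventilation. PO2 and saturation are listed but FiO2 is not a variable of its own, which makes them hard to read in a patient on oxygen. PSI and the WHO scale are absent from the written baseline visit in section 4.3.1, although Table 3 marks clinical response at screening. Date of diagnosis is not date of onset, and nothing in Table 1 stands in for centre.

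**The case against.** Simple randomisation is a valid choice in an open-label pilot, and blocking makes assignment somewhat easier to guess. Both points stand, and they make stratification an improvement rather than the repair of an invalid design.

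Three stronger readings are tempting, and the documents do not support them.

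- **That imbalance could not be corrected.** Table 1 holds several severity measures and section 5 plans a multivariate analysis, so partial adjustment is possible. Location, SOFA and symptom duration must be known to judge eligibility, and section 7.1 says that the data collection notebook gathers the clinical data the study needs; the notebook itself is not in the documents. Centre can be traced through the inclusion email, and the adverse-event form carries a centre number. What can be said is narrower: as listed, the analysis data do not contain these factors.
- **That chance imbalance biases the result.** Under true randomisation it neither biases the estimate on average nor inflates the unconditional type I error.
- **That large distortions are likely.** With 20 ICU patients, a 14:6 split or worse has binomial probability 11.5%. In a trial with 30 per arm and one third in ICU, 14:6 would shift mortality by (14/30 − 6/30) × 0.30 = 8 points. The two figures do not belong together: once the arms are fixed at 30 each, the probability is hypergeometric, 5.4%.

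Two further limits are fair. SOFA and location are tied by the eligibility rules and are close to one factor. The 7-day cap narrows the range of symptom duration. Nor do the documents establish that the trial will be small: section 4.2.10 seeks as many recipients as possible, and at N = 200 the risk is modest.

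**Conclusion.** The point holds as a worthwhile, inexpensive improvement. The text specifies unrestricted randomisation over two severity groups and several centres. Four baseline factors are missing from the database list, so direct adjustment for them is not possible from the listed data. Proxies recover part of severity, and none replaces onset date or centre.

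The chance of a gap of 10 points or more in ICU share is material up to about N = 100 and small to moderate at N = 200. Adjusting for location is worth about 8% more patients at the ICU share that the background suggests and 14% at one third. These figures rest on assumed N, ICU share and mortality, because the documents state none of them for the trial. The cost is in precision and credibility, not in average bias.

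**What to change.** 1. **Randomisation (section 4.1).** Reconcile equal probability with the 1:2 ratio first, since block composition depends on it. Then have the existing computer system use permuted blocks of varying size, stratified by ward/ICU. Add centre as a stratum only if numbers per centre allow it.
2. **Enrolment (Annex IX).** Add patient location to the inclusion email, so that the stratum is known at assignment.
3. **Data (Table 1).** Add location at baseline, SOFA, date of symptom onset and centre.
4. **Analysis (section 5).** State that the main between-arm comparison is adjusted for ward/ICU and days since onset. Add SOFA only if the sample supports another covariate.

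The cost is a system setting, one item in the email, four fields and one sentence. The drawback is slightly more predictable assignment in an open-label trial, which varying block sizes limit.

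This does not cure the rule in section 4.1 that recruits join the control group when plasma stock runs out. That departure is systematic, and it may differ by centre because plasma collected at the coordinating hospital is used there first (section 4.2.6). Recording centre would at least let that pattern be examined.

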4.2.6. Plasmapheresis of ex-convalescent donors

1. On the day of the appointment, a confirmation will be made that the selection criteria have not changed, and it will be confirmed that the analytical tests are correct.

2. Blood pressure, temperature and heart rate will be taken. Donors with a temperature greater than 37.0°C will not be accepted. Hyper/hypotensive, tachycardia or bradycardia donors will be accepted at the discretion of the Haematologist responsible for the extraction.

3. The donation will be assigned a SIN (Single identification Number; or number of donation).

4. Each of the extraction bags and the documentation related to this donation will be labelled with this NUMBER WITHOUT.

5. An extraction of 600 mL of plasma without leukocytes (< 1 x 10⁶ leukocytes per unit extracted) shall be carried out using any apheresis machine with its corresponding validated sets or kits (CE Marking) for the extraction of plasma for transfusion use. The specific protocol of each commercial house will be used.

Due to the new orders of the Ministry of Health, the Blood and Tissue Bank of the Balearic Islands will be in charge of the treatment of the sample (inactivation, classification, plasmapheresis and sending to the relevant centre). This institution is responsible for generating a plasma bank with anti-SARS-CoV2 antibodies from ex-convalescent COVID-19 donors. These donors will be selected by the Blood and Tissue Bank of the Balearic Islands as Son Llàtzer University Hospital, who will make the extractions and send the sample for treatment to the Blood and Tissue Bank. The apheresis product obtained in Son Llàtzer University Hospital shall be used as a priority in Son Llàtzer University Hospital. For the rest of the participating centres, apheresis products from the plasma bank of the blood and tissue bank will be used.

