Since from the beginning of the pandemic to the present day no effective treatment against SARS-CoV-2 infection has been found; whereas it has also been shown that the disease has a high probability of progressing rapidly into more severe forms, causing death even in vulnerable groups; whereas the forecast for late summer-start autumn 2020 is being met; whereas there are no prevalence/incidence numbers or any other type of definitive numerical data that allows canonical sample size calculations to be made; whereas the few studies that have been published on the treatment of hyperimmune plasma infection have shown a positive trend towards decreasing symptoms and severity; and that finally we continue to find ourselves in a health emergency situation; so for all these reasons this study is transformed into a multicentre study, at the request of the participating centres. Therefore, it is required, in order to estimate with maximum efficiency, the effect of this therapy, the maximum number of donors and the maximum number of possible recipients. Each case is explained below:

-For donors: it is required to collect the plasma sample from the maximum number of people who meet the requirements to be donors. This aims to create an anti-SARS-CoV-2 hyperimmune plasma bank, so that not only for this study, but for serious situations in which all the possibilities available so far have been exhausted, this therapy can be used as an alternative. The difficulty of finding suitable donors, who not only meet the requirements to be donors, but also have a sufficient antibody titration, forces us to make accurate donor lists in order to have this type of sample in sufficient quantity. Being a multicentre study, more doses of plasma will be needed to be able to supply all the centres. Considering that the ratio is 1 donor or 1 donation for each recipient.

-For recipients: as it is unknown how many patients can progress in the coming weeks/months with COVID-19, it is required to propose participation in the study to all patients who are diagnosed with COVID-19 and admitted to the plant or ICU for COVID-19 of all participating centres. In this way, the maximum number of patients can be collected, in order to cover a sufficient sample size in the two branches of comparison of the study (control and treatment). As patients are admitted, they will be proposed to participate by explanation and with the HIP, and if they sign the IC, they will become part of it.

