6. ETHICAL ASPECTS

6.1. General considerations

The study will be conducted in accordance with the standards of Good Clinical Practice and Guidelines of the International Conference on Harmonization [ICH]. In accordance with the criteria of good clinical practice, the subjects will be duly informed of all those details concerning their participation in the study and will freely give their written consent. For the use of the data contained in this register, as in any scientific research project, it will be necessary:

- Approval by the Clinical Research Ethics Committee (in Spain CEIm) local of the study author centre.
- Approval by the Scientific Committee, a body that will be constituted to give scientific performance to the database.

Scientific responsible for the registry: [name], Haematology Service, Son Llàtzer University Hospital.

The clinical trial shall be conducted in accordance with the protocol, the principles set out in the current revised version of the Declaration of Helsinki (Annex 1) and the applicable regulatory requirements, in particular the ICH Good Clinical Practice Guidelines (1996), Regulation (EU) No

536/2014 on clinical trials with medicinal products for human use, and the applicable local regulations (in Spain, the Royal Decree on Clinical Trials 1090/2015).

The ICH guidelines require the approval of the health authorities and the favourable opinion of an accredited Clinical Research Ethics Committee (in Spain CEIm) before the inclusion of patients in clinical trials. Prior to the start of the study, the protocol, informed consent, materials to be used for patient recruitment (if applicable), and any other written information in connection with the trial provided to the patient will be approved by the CEIm.

AMENDMENTS TO THE PROTOCOL:

Any modification of the study protocol shall always take the form of an amendment or addendum in writing. For its formalization, it must be issued in writing to the CEIm and the Health Authorities for approval before the proposed changes are implemented. After approval by the CEIm, the AEMPs will be immediately informed of the study, for its correct classification and obtaining supporting documentation.

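### Patients recruited while plasma is out of stock enter the control group without randomisation, so the plasma-versus-control comparison is open to bias of unknown direction.

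*Combined protocol and SAP*

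**What the plan says.** Section 4.1 describes simple random assignment by a computer system, the same in every centre, "in order to guarantee that all subjects have the same probability of belonging to the two groups". It then limits that system: "This system will be carried out whenever a plasma stock is available". For the remaining time the rule is: "In the event that the stock runs out, the recruited patients will be part of the control group".

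Other parts of the protocol bear on this:

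- **Supply.** Section 4.2.10 refers to "The difficulty of finding suitable donors, who not only meet the requirements to be donors, but also have a sufficient antibody titration", yet participation is to be offered to every patient admitted with COVID-19. Under section 4.2.6, plasma collected at the coordinating hospital goes first to its own patients. "For the rest of the participating centres, apheresis products from the plasma bank of the blood and tissue bank will be used".
- **Analysis.** Section 4.1 adds: "As treatments have been changing throughout the pandemic, when performing the final analysis, a stratified analysis will be made by type of treatment". Section 5 says that "a multivariate analysis will be performed to assess the effect of other factors such as the confusion/interaction effect", without naming covariates. It defines no analysis population.
- **Records.** Table 1 (section 4.3.3) lists no stock status, centre or randomised yes/no variable. The form in Annex V has boxes for centre and randomisation, but it covers adverse events only. Annex IX has the branch sent back after consent and describes no record of stock at that moment.

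**The concern.** A patient recruited in stock has a known chance of plasma, and a patient recruited during a stock-out has none. Placing both in one control group means that plasma patients, all recruited in stock, are compared partly with people recruited at other times and perhaps in other centres. Section 4.1 itself says that background treatment has been changing, so period may matter. Centre may matter too, given the two supply routes, but that is an inference: the text does not say whether stock is judged centrally or per centre.

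The trial is also open-label. A recruiter who knows that stock is out knows the arm before consent, which could affect who is enrolled.

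The main objective (section 3.2.1) is efficacy against standard treatment, and section 5 tests at p < 0.05. The secondary comparisons of safety, tolerance, serology and virology use the same control arm.

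**Working it through.** The protocol states no sample size, event rate or stock-out rate, so there is no figure of its own to reproduce. The following is an illustration.

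**Inputs**

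- From the protocol: the stock-out rule; the 5% significance level; the allocation. Section 4.1 describes equal probabilities but also a 1:2 control-to-treated ratio, so both are shown (probability of plasma in stock p = 1/2 or 2/3).
- Assumed: stock-out fraction s of 10%, 20% or 40%; a binary event with 15% risk in stock; 15%, 20% or 25% risk in stock-outs; no plasma effect; total N of 100 or 300; an unadjusted two-sided test.

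**Step 1. Non-randomised share of controls** = s / [s + (1 − s)(1 − p)]

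- 1:1, s = 10%: 0.10 / (0.10 + 0.45) = 18%. At s = 40%: 0.40 / (0.40 + 0.30) = 57%.
- 1:2, s = 10%: 0.10 / (0.10 + 0.30) = 25%. At s = 40%: 0.40 / (0.40 + 0.20) = 67%.

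**Step 2. Spurious risk difference** = share × risk gap

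- No gap: 0.
- 5-point gap: from 0.18 × 5 = 0.9 to 0.67 × 5 = 3.3 points.
- 10-point gap: from 0.18 × 10 = 1.8 to 0.67 × 10 = 6.7 points.

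The difference favours plasma if stock-out patients are at higher risk. It has the same size against plasma if they are at lower risk by the same gap.

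**Step 3. False-positive rate** (100,000 simulated trials per cell, pooled two-sample z test at 1.96)

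| Gap | N | Allocation | s = 10% | s = 20% | s = 40% |
|---|---|---|---|---|---|
| 5 points | 100 | 1:1 | 5.2% | 5.3% | 5.6% |
| 5 points | 100 | 1:2 | 5.5% | 6.0% | 6.9% |
| 5 points | 300 | 1:1 | 5.5% | 6.6% | 8.7% |
| 5 points | 300 | 1:2 | 6.1% | 8.1% | 11.2% |
| 10 points | 100 | 1:1 | 5.6% | 6.8% | 8.5% |
| 10 points | 100 | 1:2 | 6.8% | 9.0% | 12.5% |
| 10 points | 300 | 1:1 | 7.0% | 11.2% | 20.0% |
| 10 points | 300 | 1:2 | 9.3% | 16.7% | 29.6% |

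Repeat simulations agreed to within about 0.7 points. With no gap the rate is about 5%. It is also about 5% when only randomised patients are compared, whatever the gap.

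**Step 4. Does the planned drug stratification repair it?** Assume two drug strata, mixed 70/30 in stock and 30/70 in stock-outs, and take the expected Mantel-Haenszel risk difference, with stratum weights T × C / (T + C), where T and C are the treated and control numbers in the stratum. If drug mix explains the whole gap, the bias is removed. If it explains none, the weighted non-randomised share runs from 17.1% (1:1, s = 10%) to 60.5% (1:2, s = 40%). This leaves 0.171 × 5 = 0.9 to 0.605 × 10 = 6.1 points. If it explains half, 0.4 to 3.0 points remain.

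**The case against.** The best counter-argument is that the harm is conditional. Stock-outs must occur, those patients must be pooled, and outcomes must differ between periods or centres. The protocol gives no figure for the first or the last, and section 4.2.10 plans careful donor lists to secure enough plasma. The rule is also disclosed openly. This stands as a limit on how confidently the size can be stated. It does not remove the rule, and nothing visible prevents pooling.

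The false-positive rates come from an unadjusted test on an assumed binary outcome, whereas the plan also intends stratification and multivariate modelling. The 30% figure is the extreme corner; at N = 100 with a 5-point gap the rate is only 5–7%. Immunological outcomes are not quantified. All of this is fair. But neither planned adjustment names centre, period or stock status, and neither restores randomisation.

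Excluding stock-out controls also costs precision. At N = 100 with a 5-point gap and 1:2 allocation, pooling has the smaller root-mean-square error: 7.6 against 8.1 points at 10% stock-outs, and 8.3 against 10.0 at 40%. At N = 300 with a 10-point gap, the randomised-only comparison is better in every case examined. For a pilot, pooling with adjustment has some appeal, but as a sensitivity analysis, because its validity depends on a gap that nobody can know in advance.

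Finally, Table 1 is plainly not exhaustive: it does not list the treatment arm either. Diagnosis dates, visit dates and plasma administration dates are to be recorded, so calendar period could be reconstructed. They do not show directly which controls were randomised. Figures 1 and 2 were not available and could bear on how stock-outs are handled.

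**Conclusion.** The concern holds. Followed as written, the plan pools non-randomised with randomised controls in the comparison that answers its main objective. The in-stock patients remain properly randomised; the combined control arm is not a fully randomised comparator.

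The direction of any bias is unknown and its size cannot be derived from the protocol. It ranges from zero, if outcomes do not differ between in-stock and stock-out patients, to several percentage points under the assumptions shown. Because stock status may be impossible to recover if it is not captured at assignment, this must be corrected in the protocol rather than left to the analysis.

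**What to change.** 1. State in sections 4.1 and 5 that the main between-arm efficacy and safety comparisons use only patients assigned by the computer system while plasma was in stock.
2. Define what counts as in stock, and whether this is judged centrally or per centre.
3. Add stock status, centre and assigned-by-computer (yes/no) to Table 1, and record them at each assignment.
4. Continue recruiting during stock-outs if wished, but report those patients as a separate observational group. Label any analysis that pools them with the randomised controls as a sensitivity analysis.

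**Cost.** The change is a protocol amendment, and under section 6.1 "it must be issued in writing to the CEIm and the Health Authorities for approval before the proposed changes are implemented". It also needs analysis wording and three data fields. The main comparison has fewer controls. The relative interval width is the ratio of √(1/T + 1/C) with randomised controls only to the same quantity with all controls. Per 100 recruits:

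| Allocation | Stock-outs | Treated | Controls: randomised only / all | Interval wider by |
|---|---|---|---|---|
| 1:1 | 10% | 45 | 45 / 55 | 5% |
| 1:1 | 40% | 30 | 30 / 70 | 18% |
| 1:2 | 10% | 60 | 30 / 40 | 10% |
| 1:2 | 40% | 40 | 20 / 60 | 34% |
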